## 1. STUDY DETAILS

### 1.1 STUDY OBJECTIVES

#### Primary Objectives

The primary objective of this study is:

1. To evaluate if the subcutaneous administration of Glucagon RTU (Glucagon Injection) just before exercise, with or without a 50% reduction in basal rate insulin, compared to a 50% basal rate insulin reduction alone, prevents the occurrence of hypoglycemia (i.e., blood glucose  $\leq 70$  mg/dL; 3.89 mmol/L) measured by blood glucose meter (BGM) during and after moderate-to-high intensity aerobic exercise by adult subjects with T1D in an outpatient setting.

#### Secondary Objectives

[figure not shown]
1. To evaluate how Glucagon RTU (Glucagon Injection) contributes to prevention of hypoglycemia during exercise and post exercise recovery.
2. To evaluate the effect of Glucagon RTU (Glucagon Injection) on insulin utilization during exercise.
3. To evaluate the effect of Glucagon RTU (Glucagon Injection) on PROs: Barriers to Physical Activity in Diabetes (Type 1) (BAPAD-1), Hypoglycemia Fear Survey (HFS-II), and Hypoglycemic Confidence Scale (HCS) after 12 weeks of outpatient exercise.

## Exploratory Objectives

1. To evaluate the glycemic time in range associated with exercise sessions and post exercise.
2. To evaluate the impact of Glucagon RTU (Glucagon Injection) on the quantity of glucose tabs used over time during exercise sessions.
3. To evaluate weight loss or weight maintenance over time.
4. To examine food intake both before and after exercise.
5. To examine the effect of exercise and Glucagon RTU on overnight hypoglycemia following episodes of exercise.
6. To evaluate the effects of exercise and Glucagon RTU use upon changes in hemoglobin A1c.
7. To evaluate the intensity and duration of the frequent exercise sessions.
8. To evaluate overall frequency of aerobic exercise over study period.
9. To evaluate effects on exercise duration and intensity as well as daily activity metrics.

### 1.2 STUDY DESIGN:

This study is a randomized, placebo-controlled, double-blind, two-treatment, two-period, crossover comparison in a clinical research center (CRC) setting, followed by a randomized, placebo-controlled, partially double-blinded, 3-arm parallel comparison in an outpatient setting to evaluate the preliminary efficacy and safety of Glucagon RTU to prevent exercise-induced hypoglycemia (EIH) in adults with Type 1 diabetes mellitus (T1D), who perform regular, moderate-to-high intensity aerobic exercise.

**Figure 1. Schema of Study Design**

The CRC Stage will involve two daytime clinical research centers (CRC, or comparable setting) exercise sessions 2-28 days apart, in a morning exercise session, for the following treatment assignments:

- Insulin pump reduction (50% reduction in basal rate five minutes before exercise, for the duration of the exercise), and pre-exercise placebo injection (30  $\mu$ L vehicle), or
- Insulin pump reduction (50% reduction in basal rate five minutes before exercise, for the duration of the exercise), and pre-exercise Glucagon RTU (30  $\mu$ L active - 0.15 mg).

At Investigator discretion, the insulin pump rate can be reduced overnight based on subject's medical history for the duration of the study.

BGM assessments during CRC visits will be at -15, 0, 30, 45 and 75 minutes from the start of exercise. Venous Blood Glucose assessments (Yellow Springs Instrument [YSI] readings) during CRC visits will be at -15, 0, 15, 30, 45, 60 and 75 minutes from the start of exercise. Subjects will also wear unblinded continuous glucose monitoring (CGM) both the CRC and Outpatient Stages of the study.

The Outpatient Stage will be 12 weeks in duration during which subjects are randomized to one of three parallel treatment arms, two of which are double-blinded, and one is open-label.

During the Outpatient Stage, subjects will receive one of the following randomly assigned treatments:

- Insulin Pump reduction (50% reduction in basal rate five minutes before exercise, for the duration of the exercise), and pre-exercise placebo injection (30 µL vehicle), or
- Insulin Pump reduction (50% reduction in basal rate five minutes before exercise, for the duration of the exercise), and pre-exercise Glucagon RTU (30 µL active - 0.15 mg), or
- Pre-exercise Glucagon RTU (30 µL active - 0.15 mg) without pump changes.

Subjects will measure blood glucose using BGM at -15 and 0 minutes (just before exercise) to establish baseline, at 30 minutes of exercise, at the end of exercise, and 30 minutes post-exercise. Subjects will also wear unblinded CGM during the conduct of the study.

**Table 1. Schedule of Activities**

Assessment	Visit 1	Visit 2	Visit 3 a CRC 1	Visit 4 b CRC 2	Visits 5 to 10 Outpatient Phase	Visit 11 Follow-up f /ET
	Screening Day-28 to -3	CGM Placement Day -2 to -1	Treatment Period 1 (Days 1 a,b,c )	Treatment Period 2 Day 3 to 29 d	Treatment Period 3 Day 4 to 113 e	
Informed consent	X					
Medical History/ Demographics	X					
Inclusion/exclusion criteria	X					
Concomitant medications (including insulin pump data)	X	X	X	X	X	X
Height, weight and physical examination	X					X
12-lead ECG	X					X
Vital signs	X		X	X	X	X
Urine pregnancy test	X		X	X	X	X
Urine drug screen	X					
Hematology	X					X
Clinical chemistry	X					X
HbA1c	X					X

Assessment	Visit 1	Visit 2	Visit 3 o CRC 1	Visit 4 o CRC 2	Visits 5 to 10 Outpatient Phase	Visit 11 Follow-up f /ET
	Screening Day -28 to -3	CGM Placement Day -2 to -1	Treatment Period 1 (Days 1 a,b,c )	Treatment Period 2 Day 3 to 29 d	Treatment Period 3 Day 4 to 113 e	
Plasma Glucose	X					X
C-peptide	X					X
Immunogenicity g			X		X	X
CGM		X d	X h	X h	X h	X h
Exercise i,o			X	X		
BGM k			X	X j	X j	X j
Study drug administration			X	X l	X	
Wearable Activity Monitors (Fitbit Ionic and Polar Beat H10)			X m	X m	X n	X n
HBV, HCV, HIV Screen	X					
Outpatient Study Training				X		
Diary i			X	X	X	X
Glucose Tabs Log			X	X	X	X
Randomization			X			
8-Hour fast	X		X	X		X
Venous blood glucose (YSI)			X	X		
BAPAD-1 Questionnaire			X			X
Draize Scale			X	X		
HFS			X			X
Hypoglycemia Confidence Scale			X			X
Injection Site Discomfort Description and Duration Questionnaire			X	X		
Adverse event review	X	X	X	X	X	X

\*Visits will occur every 2 weeks during the out-patient phase. The visit window is +/- 3 days for the outpatient visits.

BAPAD-1 = Barriers to Physical Activity in Type 1 Diabetes Scale; BGM = blood glucose monitor; CRC = Clinical Research Center; CGM = continuous glucose monitor; ECG = electrocardiogram; HBV = hepatitis B

virus; HCV = hepatitis C virus; HFS = Hypoglycemia Fear Survey; HIV = human immunodeficiency virus; YSI = Yellow Springs Instrument

- a. As long as the subject has 2 days of rest between each CRC visit.
- b. Subjects will be instructed not to exercise between Visit 2 and Visit 3.
- c. Questionnaires to be completed are Barriers to Physical Activity Diabetes (Type 1) (BAPAD-1), Hypoglycemia Fear Survey (HFS) and Hypoglycemia Confidence Scale (HCS).
- d. CGM will be placed approximately 24-48 hours prior to data collection at CRC Visit 2.
- e. Collection timepoints  $\pm$  2 minutes are: -15 minutes, 0 minutes (just before initiation of exercise), and at 15, 30, 45, 60 and 75 minutes after initiation of exercise.
- f. Follow-Up occurs 14 days after the last exercise period.
- g. An immunogenicity sample will be drawn before the first dose of investigational product, every four weeks (28 days  $\pm$  2 days) and at the End of Study visit.
- h. CGM data will be downloaded.
- i. During the CRC Phase of the study, subjects will perform moderate-to-high-intensity exercise of at least 45 minutes duration, with each exercise session separated by at least 2 days during the inpatient phase of the study. During the Outpatient Phase of the study, subjects will be asked to maintain a weekly exercise average of 2 to 3 sessions weekly of at least 30 minutes. Exercise data will be downloaded from the wearable device. Data include heart rate, calories burned, daily steps, floors climbed, distance covered, active minutes.
- j. BGM Measurements will be performed at the following timepoints during CRC visits,  $\pm$  2 minutes:
  - -15 minutes (both YSI and BGM)
  - Time 0 (immediately before exercise) (both YSI & BGM)
  - 15 minutes (YSI only)
  - 30 minutes (both YSI & BGM)
  - 45 minutes (both YSI & BGM, end of exercise)
  - 60 minutes (YSI only)
  - 75 minutes (both YSI & BGM, thirty minutes after completion of exercise)
- k. BGM data will be downloaded at each patient visit.
- l. Investigational Product (IP) for first outpatient visit will be dispensed at the end of visit 4.
- m. Subject will wear both Fitbit Ionic and Polar Beat H10 heart rate sensor during this visit.
- n. Subject will wear only the Fitbit Ionic during these visits.
- o. Prior to beginning the exercise session, if the subject's blood glucose is below 100 mg/dL the subject is allowed to take dextrose tabs (e.g., 2-4 tabs) to raise the blood glucose, and the blood glucose verified to be within 100-180 mg/dL (5.56 – 10 mmol/L). The number of dextrose tabs and time administered are recorded. Prior to beginning the exercise session, if the blood glucose is  $>180$  mg/dL after repeat test, then the investigator may treat with an intravenous (IV) bolus dose of regular insulin, per discretion, to bring the subject into the required blood glucose range. Before initiating study treatment, at least 40 minutes should have passed from the last dose of administered insulin and the subject's glucose level should be within the range of 100 to 180 mg/dL. At discretion, the investigator may reschedule the visit to occur after a minimum wait of 24 hours. The visit should be re-scheduled so it occurs within the originally defined visit window. For example, a rescheduled Visit 3 (CRC 1) should occur within 28 days of Visit 1 (Screening), while a rescheduled Visit 4 (CRC 2) should occur within 28 days of a completed Visit 3 (CRC 1).

### 1.3 DETERMINATION OF SAMPLE SIZE

The primary endpoint of the study is the incidence of hypoglycemia (glucose  $\leq$  70 mg/dL (3.89 mmol/L)) associated with an exercise session, which occurred within the 12-week outpatient follow-up, as measured by BGM. The null hypothesis is that there is no difference between the treatment groups in the incidence of exercise-associated hypoglycemia, and the alternative is there is a difference between the treatment groups in terms of the incidence of exercise-associated hypoglycemia. With an effect size estimate of 0.262 (variance of means 59, common standard deviation 15), 80% power and an alpha of 0.05, using a one-way analysis of variance, 14 subjects per treatment group in the Outpatient Stage is required. Accounting for 15% attrition, a total of 48 subjects will be randomized.

#### 1.3.1 Randomization and Blinding

The study statistician will create the randomization schedule for the study. The randomization assignment for the subject will be conducted once at the time of enrollment and confirmation of eligibility. The CRC assignments will be by random assignment during the first session to either Glucagon RTU or Placebo. At the second session, the subject will be crossed over to the other treatment assignment. At the completion of the CRC visits, the subject will then have his/her treatment assignment applied for the parallel group study.

The cross-over study is blinded to the extent possible since all subjects will receive both Glucagon RTU and placebo. All staff, subjects and study team members will know that the subject will receive both study treatments during the CRC sessions. During the outpatient study, two of the treatments will be blinded to the study staff, subjects and Sponsor. One arm of the study will be open label. It is imperative for the study staff to remain blinded to treatment assignment prior to randomization and during the study treatment periods as not to bias the outcome.

Glucagon RTU and Placebo will be prepared and administered so that the two will be indistinguishable.

Blinding of study treatment is critical to the integrity of this clinical trial. It is expected that in the majority of cases, AEs can be properly managed without the need for unblinding. However, in the event of a medical emergency in which knowledge of an individual subject's treatment

assignment is considered critical to the subject's management, the treating physician may unblind the treatment assignment. The investigator should contact the responsible Medical Director to discuss the subject and circumstances requiring the unblinding. The blind will be broken only for the specific subject under discussion. The Sponsor will remain blinded to the treatment assignment. Every effort will be made to restrict knowledge of the treatment assignment to the investigator only.

## 2. STATISTICAL AND DATA ANALYSIS CONSIDERATION

The statistical analyses will be performed by EmpiriStat, Inc., using SAS Version 9.3 (or higher). All tables, listings and figures (TLFs) will be produced in landscape format. In general, all data will be listed by the subject and visit/time point where appropriate.

Data will be summarized by treatment/treatment sequence and by period where appropriate. The total number of subjects in the study group (N) under the stated population will be displayed in the treatment sequence/treatment header of summary tables.

Data will be summarized using descriptive statistics for continuous variables. Unless otherwise stated, descriptive statistics will include number of subjects, mean, standard deviation, minimum, median and maximum. In case of  $n < 2$ , where n indicates the number of evaluable subjects at the particular time point, only n, mean, minimum and maximum will be displayed. The statistic "Missing" will also be evaluated by enumerating the number of missing entries/subjects, if any at that visit, and presented as a summary statistic only for the resulting time points.

**Decimal Precision Convention:** The minimum and maximum statistics will be presented to the same number of decimal places as the original data. The mean and median will be presented to one more decimal place than the original data, whereas the standard deviation will be presented to two more decimal places than the original data.

In summary tables of categorical variables, counts and percentages will be used. The count [n] indicates the actual number of subjects with a particular value of a variable or event, which should always be less than or equal to the total number of subjects in the respective treatment sequence [N]. Percentage will be obtained by:  $\% = (n/N)*100$ . Unless otherwise stated, all percentages will be expressed to one decimal place.

The closest non-missing measurement (whether from scheduled or unscheduled visit) taken prior to the first dose administration will be considered as the baseline value. The Post-baseline values are defined as measurements taken after the first administration of study drug. For summarizing vital signs follow-up visits, screening value will be considered as baseline, and change from baseline to follow-up visit is the change in measurement from baseline (screening) to follow-up visit. For other visits, baseline is the measurement taken at pre-dose in each period and change in measurement from baseline (pre-dose) to each post-dose in each period.

The following conventions will be applied to analyses/data presentation:

All dates will be displayed in DDMMYY format.

All unscheduled visit data will be presented in Listings, and last repeated unscheduled visit data (if applicable) which will be flagged as analysis value will also be used in summarizing data for Tables and Figures.

For Listings, data will be presented by subject, sequence, treatment, period, parameter, assessment date in chronological order, but not limited to the above variables. The number of variables presented in each listing can vary. Please refer to the Mock tables, listings and figures.

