### **Laboratory:**

Laboratory evaluation results for observed values and change from baseline will be summarized descriptively by treatment and visit using Safety Population. Unless otherwise specified, all continuous laboratory data will be summarized using descriptive statistics (n, mean, SD, median, min, and max) for each scheduled study assessment as well as change from baseline by parameter class (Hematology and Biochemistry). Abnormal laboratory values will be summarized using frequency and percentage using the safety population.

Hematology and Chemistry data will be summarized by displaying shifts from baseline value (low/normal/high or Normal/Abnormal as applicable) to subsequent assessment.

Safety laboratory data (Hematology and Chemistry) will be listed by timepoint for each parameter and subject. All abnormal values will be flagged on the listing. Serology, HbA1c and C-peptide data will also be listed.

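### Using the last unscheduled repeat as the analysis value, with no worst-value rule, can drop abnormal Visit 11 laboratory and ECG results from the safety tables

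*SAP*

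**What the plan says.** SAP section 2 sets a general convention for unscheduled data. First, "All unscheduled visit data will be presented in Listings". The sentence then adds that "last repeated unscheduled visit data (if applicable) which will be flagged as analysis value will also be used in summarizing data", and it names tables and figures as the place. Baseline has its own selection rule in the same section, so this convention acts mainly on post-baseline data.

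The Laboratory part of SAP 4.3.9 defines three kinds of output:

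- Continuous summaries are given "for each scheduled study assessment as well as change from baseline by parameter class (Hematology and Biochemistry").
- For abnormal results, "Abnormal laboratory values will be summarized using frequency and percentage using the safety population". Which records count is not stated.
- Shift tables show "shifts from baseline value (low/normal/high or Normal/Abnormal as applicable) to subsequent assessment". No worst post-baseline category is defined.

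For the listings, "All abnormal values will be flagged on the listing". The 12-lead ECG part of SAP 4.3.9 counts the overall evaluation in three categories (normal, abnormal not clinically significant, abnormal clinically significant) at Screening and end of study.

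In the Schedule of Activities (Protocol 2.3 and SAP Table 1), hematology, clinical chemistry and ECG are each marked only at Screening and at Visit 11 Follow-up/ET.

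**The concern.** A repeat laboratory test or ECG is usually ordered because a scheduled result was abnormal. If the last of those repeats becomes the value for the visit, the tables tend to show the resolved finding rather than the one that prompted the retest. Most trials have other scheduled visits at which the abnormality might still be seen. Here there is one post-baseline draw and one post-baseline ECG, so no other scheduled value would show it.

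The outputs at stake are SAP Tables 14.3.4.2.3 (abnormal laboratory findings), 14.3.4.3.1 (ECG findings), and 14.3.4.4.1 and 14.3.4.4.2 (hematology and chemistry shifts). They bear on stated safety endpoints: Protocol 5.2.4 names laboratory change from Baseline and the number of abnormal and clinically significant ECG results. Elsewhere the SAP leans the cautious way. Section 2.2 treats events with uncertain dates as treatment-emergent, missing severity as severe and missing relationship as related. The repeat convention tends in the opposite direction.

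**Working it through.** The documents give no figure for this point, so there is nothing to reproduce. The check is a comparison of rules, followed by an illustration of size.

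**Step 1: one subject under each reading.** Suppose Visit 11 is HIGH, the first repeat HIGH and the last repeat NORMAL.

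| Rule | What the shift table shows |
|---|---|
| A. Last repeat replaces the Visit 11 value | NORMAL; the abnormal result is gone |
| B. Last repeat is added to the Visit 11 value | HIGH and NORMAL; two records for one visit |
| C. Worst post-baseline value | HIGH |

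**Step 2: which reading fits the SAP.** The only record the sentence flags as the analysis value is the last repeat. SAP section 2 defines a categorical count as a number of subjects. A shift table or a three-category ECG table normally holds one value per subject per visit. Reading A fits that structure. Reading B could put one subject in two categories at the same visit, and the SAP has no rule for that. Reading A is therefore the natural one, though it is not explicit. Reading B would need a correction too.

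**Step 3: size under reading A.** Inputs:

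- 48 subjects randomized (Protocol 12.2, SAP 1.3) and 1:1:1 allocation (Protocol 8.5), so 48 / 3 = 16 per arm.
- p, the share of subjects with an abnormal Visit 11 result: assumed 5% to 20%.
- q, the share of those who are normal on the last repeat: assumed 25% to 75%.
- Every abnormal result is retested, and all 48 subjects have the Visit 11/ET assessment: both assumed.

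Formulas: abnormal per arm under rule C = 16p; under rule A = 16p(1 − q); subjects losing the abnormal result = 48pq; chance that at least one does = 1 − (1 − pq)^48.

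| p | Rule C per arm | Rule A per arm (q = 25% to 75%) | Lost of 48 (q = 25% to 75%) |
|---|---|---|---|
| 5% | 16 × 0.05 = 0.8 | 0.6 to 0.2 | 0.6 to 1.8 |
| 10% | 16 × 0.10 = 1.6 | 1.2 to 0.4 | 1.2 to 3.6 |
| 20% | 16 × 0.20 = 3.2 | 2.4 to 0.8 | 2.4 to 7.2 |

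The chance of at least one loss runs from 1 − (1 − 0.0125)^48 = 0.45 to 1 − (1 − 0.15)^48 > 0.99. One subject is 1/16 = 6.25 percentage points of an arm, so a single reclassified subject visibly changes a percentage.

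**The case against.** The strongest reply is that replacement is inferred. The SAP says the last repeat will also be used. That may mean in tables as well as listings, or in addition to the scheduled value, and nothing says the scheduled value is dropped. The continuous laboratory summaries are tied to scheduled assessments and the ECG table to Screening and end of study, which suggests the general convention need not override scheduled values. The SAP also refers to mock tables that are not among the documents and may settle record selection. This stands as a reason to state the consequence conditionally. It does not remove the gap, because neither reading comes with a rule that keeps the abnormal finding in a table with one value per subject.

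A reader might infer more, and the documents do not support it:

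- That the abnormality certainly leaves the abnormal-laboratory table. SAP 4.3.9 does not restrict that table to flagged records, and counting every abnormal value would fit its text.
- That it survives only in listings. Protocol 9.3.1.1 lets a laboratory abnormality qualify as an adverse event, and SAP 4.3.9 tabulates adverse events. That route depends on the investigator reporting it.
- That the bias always runs toward normal. A last repeat that is abnormal after a normal scheduled value would be shown as abnormal.

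The documents also give no retest rule, so repeating until the value settles is an assumption. Protocol 9.3.1.4 lends it partial support, since adverse events are followed to resolution or medical stability; but such cases would already be in the AE tables. Finally, these tables are descriptive, the rule applies to all arms alike, and no efficacy conclusion depends on it.

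**Conclusion.** The point holds in conditional form. The SAP selects the last repeated unscheduled value for tables and figures and sets no worst-value or any-post-baseline rule. If that value represents Visit 11/ET, an abnormal result that normalizes on retest can drop out of the shift tables and the ECG evaluation table, and possibly out of the abnormal-laboratory table. The listings keep it, and the AE tables do if it was reported as an event.

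The expected direction is toward fewer abnormalities, on the assumption that abnormal results are the ones usually repeated. The range of 0.6 to 7.2 subjects of 48 rests entirely on the assumed p and q, on full retesting and on replacement; it is not an estimate from the documents. The primary analysis, sample size and alpha are untouched. The change is worth making because the tables concern stated safety endpoints and the correction costs very little.

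**What to change.** In SAP section 2, state that by-visit summaries use the scheduled value, and that a repeat replaces it only when the scheduled sample is missing or technically invalid. In SAP 4.3.9, state that the abnormal-laboratory, shift and ECG-evaluation tables use each subject's worst post-baseline value from scheduled and unscheduled assessments together. For parameters with both low and high categories, define worst in each direction so that the choice is not left to programming. Keep the listings as planned, and align the mock tables with the new text.

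The cost is a few sentences and one more programming flag. Reported abnormality rates may be slightly less favourable and may include some single abnormal values that were not confirmed on retest. A table footnote can say so, and the listings show the repeats.
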